The information contained in this protocol is proprietary and provided to me in confidence, and may not be disclosed to any other party, in any form, without prior authorization from MEI Pharma, Inc., except to the extent necessary for the conduct of the study at this study site.

Principal Investigator:

Signature

Date

Printed Name

Institution

PROTOCOL SYNOPSIS

TITLE

A Phase 1, Open-label, Study of Voruciclib in Subjects with Relapsed and/or Refractory B-Cell Malignancies or Acute Myeloid Leukemia After Failure of Prior Standard Therapies and Voruciclib in Combination with Venetoclax in Subjects with Relapsed and/or Refractory Acute Myeloid Leukemia

PROTOCOL NUMBER

ME-522-001

SUBJECT POPULATION

Subjects with relapsed and/or refractory B-cell malignancies (Follicular lymphoma [FL], mantle cell lymphoma [MCL], marginal zone lymphoma [MZL], small lymphocytic lymphoma [SLL], chronic lymphocytic leukemia [CLL], and diffuse large B-cell lymphoma [DLBCL]) or relapsed and/or refractory acute myeloid leukemia (AML)

INVESTIGATIONAL PRODUCT

The active pharmaceutical ingredient, voruciclib, is (+)-trans-3-[2[(2-Chloro-4-trifluoromethyl-phenyl)-5,7-dihydroxy-8-(2-hydroxymethyl-1-methyl-pyrrolidin-3-yl)-chromen-4-one, and is available in 2 salt forms, hydrochloride and malonate.

Voruciclib is a potent oral cyclin-dependent kinase (CDK) inhibitor that indirectly suppresses the function of the pro-survival Myeloid cell leukemia protein (Mcl-1).

Voruciclib is provided as 50 and 100 mg capsules (hydrochloride salt) or tablets (malonate salt) for oral administration. The malonate salt tablet is the only formulation that will be used in the voruciclib and venetoclax ([Venclexta®](#)) combination portion of this study.

Other co-administered drug (combination study cohorts in AML subjects only, per this amendment [Amendment 11]):

Voruciclib will be administered, in some cohorts, in combination with the Bcl-2 inhibitor venetoclax. Venetoclax is approved by the US Food and Drug Administration for the treatment of adults with CLL or SLL, and in combination with azacitidine, decitabine, or low-dose cytarabine for the treatment of newly diagnosed AML in adults aged 75 years or older, or who have comorbidities that preclude use of intensive induction chemotherapy.

Venetoclax is available commercially as 10 mg, 50 mg, and 100 mg tablets for oral administration.

STUDY OBJECTIVES

Primary Objectives

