4.3.2. Dose Cohort Evaluation of Voruciclib + Venetoclax Combination Therapy in AML

Combination therapy with voruciclib and venetoclax will be evaluated in AML subjects only, and only subsequent to the determination of the safety, tolerability, and minimum biologically effective dose of voruciclib monotherapy in AML subjects. Dose escalation of voruciclib in the combination cohorts will be informed by the safety, tolerability, and PK results and require the approval of the SRC.

The voruciclib monotherapy results in AML subjects as of 21 September 2021 demonstrated the dose level voruciclib 200 mg IS_{2w,2w} (Cohort 8a) as safe, had antitumor activity in some patients, and achieved steady state (Day 8) pre-dose plasma concentrations of 0.9 µM and C_{max} of 1.5 µM (concentrations shown to be active in non-clinical models in AML and CLL). The Sponsor determined that 200 mg is a safe and minimum biologically effective dose, and in consultation with the SRC, the decision was made to stop voruciclib dose escalation because continued dose escalation solely to determine the MTD of single agent voruciclib in AML may expose subjects to potential toxicity, and single-agent CDK9 inhibitors are unlikely to induce durable responses in AML. A more clinically meaningful approach would be to evaluate voruciclib in combination with venetoclax, and to conduct the evaluation of additional dose levels with the combination therapy.

Amendment 11 – IS_{2w,2w} Dosing Schedule

Voruciclib dosing in combination with venetoclax will utilize the IS_{2w,2w} dosing schedule, starting with the dose level of voruciclib 50 mg QOD (Cohort 12) and escalating as per [Table 3](#). The voruciclib starting dose of 50 mg QOD was selected because it is 4 dose levels lower than 200 mg QD, the dose established to be safe as a monotherapy on IS_{2w,2w} in AML. The dose of 50 mg is 25% of the highest dose studied in AML, and for which no DLTs were reported, to take into account potential drug interaction with venetoclax and the first introduction in clinical studies of the voruciclib malonate salt tablets (see [Section 4.3.2.2](#) for details).

The dose levels of voruciclib to be evaluated range from 50 mg to 350 mg administered IS_{2w,2w}. For reference, the MTD of voruciclib in Phase 1 studies in solid tumors was 600 mg when

administered daily for 14 days in a 21-day cycle and 350 mg daily when administered continuously.

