Only the tablet formulation containing the voruciclib malonate salt will be used in the voruciclib plus venetoclax combination group.

Table 3: Dose Cohorts with Combination Voruciclib + Venetoclax (Amendment 11)

Cohort Dose Level	Doses and Schedule
12	voruciclib 50 mg QOD, administered IS _{2w,2w} + venetoclax administered QD × 28 days
13	voruciclib 50 mg QD, administered IS _{2w,2w} + venetoclax administered QD × 28 days
14	voruciclib 100 mg QD, administered IS _{2w,2w} + venetoclax administered QD × 28 days
15	voruciclib 150 mg QD, administered IS _{2w,2w} + venetoclax administered QD × 28 days
16	voruciclib 200 mg QD, administered IS _{2w,2w} + venetoclax administered QD × 28 days
17	voruciclib 250 mg QD, administered IS _{2w,2w} + venetoclax administered QD × 28 days
18	voruciclib 300 mg QD, administered IS _{2w,2w} + venetoclax administered QD × 28 days
19	voruciclib 350 mg QD, administered IS _{2w,2w} + venetoclax administered QD × 28 days

Abbreviation: QOD = once every other day

At the completion of the DLT period for each cohort, decisions to escalate in subsequent cohorts will be guided by SRC review of all available safety data, PK and PD data.

For Cohort 12, the dosing of voruciclib will be Days 3, 5, 7, 9, 11, and 13 of Cycle 1, and Days 1, 3, 5, 7, 9, 11, and 13 of Cycle 2 and beyond.

Dose escalation to the next cohort will be initiated after 3 subjects have completed 1 cycle with no reported DLTs, or after 6 subjects have completed 1 cycle with no more than 1 DLT (as defined in [Section 4.4](#)) and with the approval of the SRC after review of safety from the cohort under review.

Intra-patient dose escalation to the next dose in Cycle 2 or later cycle is allowed at the discretion of the investigator and after consultation with the Sponsor if the next dose level has been declared safe by the SRC. More specifically, a subject enrolled at a dose level X may have their dose escalated to the next dose level X + 1 after completing Cycle 1 without a DLT.

Dose escalation proceeds until assessment of clinical and PK parameters by the SRC establishes the safe BED for voruciclib in combination with venetoclax. More specifically, a voruciclib dose in combination with venetoclax that meets the following criteria:

- DLT not to exceed 1 in 6 patients, overall response rate (ORR) $\geq 30\%$, as compared to historical ORR of 19% with 400-800 mg venetoclax alone in relapsed/refractory AML ([Konopleva 2016](#)), and

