4.3.2.1. Administration Schedules and Doses of Voruciclib + Venetoclax

Amendment 11 – IS_{2w,2w} Dosing Schedule

For Cycle 1 in combination cohorts 12–19, the dosing will be as follows ([Table 5](#)):

- Venetoclax will be ramped up starting with 100 mg on Day 1, 200 mg on Days 2–21, then 400 mg administered as a single agent on Days 22–28.
- Voruciclib dosing will be administered on Days 3–14 at the appropriate Cohort Dose ([Table 3](#)).

For Cycle 2 and beyond, the dosing will be as follows:

- Venetoclax 200 mg will be administered on Days 1–21, and 400 mg administered as a single agent on Days 22–28.
- Voruciclib at the cohort dose ([Table 3](#)) on Days 1–14.

Venetoclax should be taken with a meal and water. When both venetoclax and voruciclib are to be taken, venetoclax should be taken first with a meal followed by voruciclib at least 2 hours later (e.g., meal completed at 8 a.m. with venetoclax, dose of voruciclib taken after 10:00 a.m.). Voruciclib tablets must not be chewed, crushed, or broken.

Table 5: Administration Schedules of Voruciclib given in Combination with Venetoclax (IS_{2w,2w})

Administration Schedule of Voruciclib IS _{2w,2w} and Venetoclax per 28-day Cycle					
Cycle 1	Day 1	Day 2	Days 3 to 14	Days 15 to 21	Days 22 to 28
Venetoclax	100 mg	200 mg	200 mg	200 mg	400 mg
Voruciclib QD	-	-	Cohort dose	None	None
Voruciclib QOD ^a	-	-	50 mg ^a	None	None
Cycle 2 and beyond	Days 1 to 14		Days 15 to 21		Days 22 to 28
Venetoclax	200 mg		200 mg		400 mg
Voruciclib QD	Cohort dose		None		None
Voruciclib QOD ^a	50 mg ^a		None		None

Abbreviation: QOD = once every other day

^a For cohort 12, the dose of voruciclib will be 50 mg once every other day (QOD) on Days 3, 5, 7, 9, 11, and 13 of Cycle 1, and on Days 1, 3, 5, 7, 9, 11, and 13 of Cycle 2 and beyond.

Amendment 12 – IS_{3w,1w} Dosing Schedule

For Cycle 1 in combination cohorts 21–25, the dosing will be as follows (Table 6):

- Venetoclax dose will be ramped up starting with 100 mg on Day 1, 200 mg on Days 2–21, then 400 mg administered as a single agent on Days 22–28.
- Voruciclib dosing will be administered on Days 3–21 at the appropriate Cohort Dose (Table 4).

For Cycle 2 and beyond, the dosing will be as follows:

- Venetoclax 200 mg will be administered on Days 1–21, and 400 mg administered as a single agent on Days 22–28.
- Voruciclib at the cohort dose (Table 4) will be administered on Days 1–21.

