For the combination cohorts on IS_{2w,2w} (Amendment 11), the starting dose of voruciclib in Cohort 12 is 50 mg QOD, which will further reduce voruciclib exposure to account for potential increases (if any) in bioavailability of the new malonate tablet formulation during the exposure cycles. Dosing in Cohort 13 (50 mg QD) will commence only after the safety of QOD dosing of voruciclib with venetoclax in Cohort 12 is established.

For the first two dose levels (50 mg QOD and 50 mg QD), for which voruciclib dose reduction is not possible, voruciclib will be temporarily stopped if the subject requires treatment with an azole antifungal due to the potential of drug-drug interactions and increase exposure to voruciclib. Subjects who recover from the infection can restart voruciclib after the last dose of the azole antifungal (after at least 5 times the half-life of the agent). For subjects receiving

voruciclib at or above 100 mg, a dose reduction by 1 dose level will be required for concomitant treatment with an azole or other strong CYP3A4 inhibitor.

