9.14.2. Voruciclib + Venetoclax Combination Therapy

Pre-dose specimens should be drawn within 2 hours prior to dosing and post-dose within +30 minutes of designated post-dose sampling times.

Blood samples for characterization of **voruciclib PK** will be collected in Cohorts 12–19 and 21–25 as shown in [Table 14](#) and [Table 15](#), relative to dosing of voruciclib.

Table 14: PK Sample Collection for Voruciclib, Cohort 12 (QOD Dosing)

Cycle	Day	Time of Collection	
		Pre-dose	Post-dose
1	3	X	2, 4, 6 hours
	4*	-	approximately 24 hours after Day 3 dose
	8	-	approximately 24 hours after Day 7 dose
	13	X	2, 4, 6 hours
	14	-	approximately 24 hours after Day 13 dose
	21	anytime during clinic visit	
2	1	X	-
4, 6	1, 14 (± 3 days)	anytime during clinic visit	
Every 3 cycles thereafter	1, 14 (± 3 days)	anytime during clinic visit	

* Day 4 sample to be collected only if the subject is able to visit the clinic.

Table 15: PK Sample Collection for Voruciclib, Cohorts 13–19 and 21–25 (QD Dosing)

Cycle	Day	Time of Collection	
		Pre-dose	Post-dose
1	3	X	2, 4, 6 hours
	4*	X (approximately 24 hours after Day 3 dose)	-
	8	X (approximately 24 hours after Day 7 dose)	-
	14	X	2, 4, 6 hours
	15	-	approximately 24 hours after Day 14 dose
	21	anytime during clinic visit	
2	1	X	-
4, 6	1, 14 (± 3 days)	anytime during clinic visit	
Every 3 cycles thereafter	1, 14 (± 3 days)	anytime during clinic visit	

* Day 4 sample to be collected only if the subject is able to visit the clinic.

Drug-Drug Interaction (DDI) Assessment: Voruciclib exposures (when co-administered with venetoclax) will be compared to historical single agent data to assess DDI and the effect of venetoclax on voruciclib PK.

Blood samples for characterization of **venetoclax PK** will be collected in Cohorts 12–19 and 21–25 as shown in [Table 16](#) and [Table 17](#), relative to dosing of venetoclax.

Table 16: PK Sample Collection for Venetoclax, Cohort 12 (QOD Dosing)

Cycle	Day	Time of Collection	
		Pre-dose	Post-dose
1	13	X	2, 4, 6, 8 hours
	14	X (approximately 24 hours after Day 13 dose)	-
	21	anytime during clinic visit	
2	1	X	2, 4, and 6-hours post-dose of venetoclax (voruciclib to be dosed 6 hours after venetoclax administration, after completion of the 6- hour sample collection)
4, 6	1, 14 (± 3 days)	anytime during clinic visit	
Every 3 cycles thereafter	1, 14 (± 3 days)	anytime during clinic visit	

Table 17: PK Sample Collection for Venetoclax, Cohorts 13–19 and 21–25 (QD Dosing)

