10.5. Pharmacokinetic Analyses

For all monotherapy cohorts, the PK of voruciclib will be summarized by descriptive statistics. Pharmacokinetic parameters will be estimated, where appropriate, by non-compartmental analysis using statistical computer packages as specified in the statistical analysis plan. Graphic evaluation will be used for data analysis where appropriate. Pharmacokinetics and fit will be evaluated graphically; modeling will also be used if sufficient data are available.

For the combination treatment cohorts, the PK of voruciclib and venetoclax will be summarized separately, as above and compared to historical data.

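### The planned comparison of combination voruciclib exposure with historical single-agent exposure mixes the new malonate tablet with the venetoclax effect, so the exposure ratio alone cannot be reported as a drug interaction

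*Protocol*

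**What the plan says.** Protocol 9.14.2 plans that voruciclib exposures in combination "will be compared to historical single agent data to assess DDI and the effect of venetoclax on voruciclib PK". Protocol 10.5 repeats this for both drugs: "the PK of voruciclib and venetoclax will be summarized separately, as above and compared to historical data". Neither section mentions formulation.

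On formulation, the Protocol Synopsis states: "Voruciclib is provided as 50 and 100 mg capsules (hydrochloride salt) or tablets (malonate salt) for oral administration". Section 4.3.2 adds: "Only the tablet formulation containing the voruciclib malonate salt will be used in the voruciclib plus venetoclax combination group". The same section gives, as one reason for the low starting dose in Cohort 12, "the first introduction in clinical studies of the voruciclib malonate salt tablets". Section 4.15 says the every-other-day start is meant "to account for potential increases (if any) in bioavailability of the new malonate tablet formulation". SAP 3.4 likewise describes capsules in general and malonate tablets for the combination cohorts.

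On timing, section 4.3.2.1 starts venetoclax on Day 1, and for the two-weeks-on schedule says: "Voruciclib dosing will be administered on Days 3–14 at the appropriate Cohort Dose". Tables 5 and 6 show venetoclax 200 mg on every scheduled voruciclib day, in Cycle 1 and later, on both schedules.

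Two further analyses lie partly outside these documents. Section 9.14.2 plans a pooled population PK analysis of voruciclib across trials, and SAP 8.8 leaves PK to a separate plan.

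**The concern.** The comparison is meant to isolate one change, the addition of venetoclax. The two groups differ by a second change, salt and dosage form, and the protocol itself treats that change as able to alter exposure. If 9.14.2 is followed as written, any formulation effect on exposure will be labelled a venetoclax effect.

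The interaction is a live question. Section 4.3.2.2 calls voruciclib a P-gp substrate and, for logistical reasons, departs from the separation in time that it cites from the venetoclax label. Section 4.14.1 calls voruciclib a CYP3A4 substrate. A P-gp interaction in the gut would act on bioavailability, as a change of tablet would. What is at stake is the meaning of a reported interaction estimate for a secondary PK objective.

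**Working it through.** **1. Which formulation is historical?** Section 9.14.2 does not say. If the combination part is the tablet's first clinical use (4.3.2), earlier single-agent data are capsule data. Protocol 10.1 gives 40 monotherapy subjects with enrolment complete. SAP section 4 counts 33 subjects, and 6 in the monotherapy expansion, by the start of Amendment 11. So 40 − 39 = 1 monotherapy subject was enrolled later, or 40 − 33 = 7 if the 6 are within the 33. Nothing says that any of them took tablets.

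**2. What can be estimated?** On the log scale, take an intercept, a tablet effect and a venetoclax effect. The plan supplies two kinds of observation:

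- historical: capsule, no venetoclax, row (1, 0, 0)
- combination: tablet, venetoclax, row (1, 1, 1)

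The rank is 2 for 3 parameters. Adding every Cycle 1 voruciclib day repeats the second row and leaves the rank at 2. A tablet-without-venetoclax row (1, 1, 0) would raise it to 3, but none is scheduled.

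**3. Size.** Observed exposure ratio = F × R, with F = tablet/capsule bioavailability and R = venetoclax effect. The documents give no F. Because 4.15 mentions only increases, assume F from 1.0 to 1.4:

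- R = 1.0 reads as 1.0 × 1.0 = 1.0 up to 1.4 × 1.0 = 1.4
- R = 1.4 reads as 1.0 × 1.4 = 1.4 up to 1.4 × 1.4 = 1.96
- an observed 1.4 fits any R from 1.4/1.0 = 1.4 down to 1.4/1.4 = 1.0

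**4. Sample size does not help.** A simulation assumed no interaction, a CV of 40% and 40 historical subjects (16 + 24, the two groups in 4.3.2.2). It counted how often the 90% confidence interval for the ratio excludes 1:

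| Combination subjects | F = 1.0 | F = 1.25 |
|---|---|---|
| 12 | 10% | 53% |
| 40 | 10% | 83% |
| 200 | 10% | 96% |

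**5. What does survive.** Section 4.3.2.2 uses accumulation ratio = 1/(1 − exp(−k·τ)). F does not appear in it, because it multiplies exposure on both days and cancels. First reproduce the plan's figures from half-life = 24 × ln 2 / (−ln(1 − 1/ratio)): a ratio of 2.06 gives 25.0 h and 2.77 gives 37.1 h, against the stated 24 to 36 h.

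Table 15 samples Day 3 and Day 14 pre-dose and at 2, 4 and 6 h, with 24-hour samples on Days 4 and 15. Day 4 is taken only if the subject can attend. So the ratio can be formed within subjects who have the Day 4 sample. Cohort 12 is dosed every other day, so its ratio refers to a different τ.

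Sensitivity is limited. Suppose venetoclax divided clearance by an assumed 1.4 with volume unchanged. A half-life of 24 h becomes 24 × 1.4 = 33.6 h. Accumulation goes from 1/(1 − 2^(−24/24)) = 2.00 to 1/(1 − 2^(−24/33.6)) = 2.56, a factor of 1.28. The two historical values already differ by 2.77/2.06 = 1.34.

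**The case against.** The strongest counter-argument is that confounding of exposure level is not confounding of everything. A reader might infer that nothing at all can be learned about the venetoclax effect on voruciclib. The documents do not support that: the accumulation ratio is free of a constant bioavailability factor and uses samples already planned. This stands. It is only a partial answer, because accumulation cannot show an absorption-level effect and is not the measure that 9.14.2 names.

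A reader might also infer that a venetoclax-driven rise in exposure could be hidden. That needs a tablet with lower bioavailability than the capsule, and section 4.15 speaks only of increases. With F at or above 1, such a rise is exaggerated, not masked.

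Nor does the protocol promise a formal interaction conclusion or tie this comparison to dosing advice. It sets no test or no-effect bound, section 10.5 is descriptive, and SAP 7.9 calls the study exploratory. Even so, the stated purpose of the comparison in 9.14.2 is to assess an interaction, and descriptive reporting does not remove the misattribution.

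Finally, the population PK analysis or the separate PK plan may deal with formulation. That is possible, but pooling separates the two effects only if tablet data without venetoclax are in the pool, and the documents name none. Table 11 allows venetoclax to be shortened to Days 1 to 14 after repeated cytopenia, which could leave some subjects in Cohorts 21 to 25 with tablet-only days. Those days would be unplanned, selected by toxicity and sparsely sampled.

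**Conclusion.** The concern holds for exposure level. The ratio of combination to historical voruciclib AUC, Cmax or trough estimates the joint effect of the malonate tablet and venetoclax, and by itself cannot be reported as a drug interaction. Under an assumed bioavailability ratio of 1.0 to 1.4, the absence of any interaction would read as 1.0 to 1.4.

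This rests on two points: the inference that the historical data are capsule data, and an assumed range for a ratio that the documents do not give.

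The conclusion does not extend to a clearance effect, which stays partly assessable through accumulation. It also leaves two things untouched. The trough criterion of 1 to 1.5 µM uses observed concentrations directly. The effect of voruciclib on venetoclax has its own within-subject contrast, Cycle 2 Day 1 against Cycle 1 Day 14.

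**What to change.** - **Protocol 9.14.2, voruciclib DDI sentence.** State the formulation of the historical data. Replace the sentence with, for example: *Voruciclib exposure in combination will be compared descriptively with historical single-agent data; the exposure ratio will be reported as the combined effect of the malonate tablet and venetoclax, not as a drug interaction.*
- **Protocol 9.14.2, addition.** Compare the within-subject accumulation ratio (Day 14 against Day 3, in subjects with the Day 4 sample) with historical values, as the formulation-independent look at clearance.
- **Pooled population PK model.** Include formulation as a covariate. Estimate a venetoclax effect on voruciclib bioavailability only if single-agent tablet data are in the pool; otherwise report one combined parameter.
- **Protocol 10.5.** Keep the sentence that summarises both drugs and add this qualification for voruciclib only, so that the venetoclax summary is not lost.

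The cost is a few sentences in the protocol and matching text in the separate PK plan, with no new samples or visits. The downside is that the trial gives up an interaction claim based on exposure level, which its data cannot support.

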Cycle	Day	Time of Collection	
		Pre-dose	Post-dose
1	14	X	2, 4, 6 and 8-hours
	15	X (approximately 24 hours after Day 14 dose)	-
	21	anytime during clinic visit	
2	1	X	2, 4 and 6-hours post-dose of venetoclax (voruciclib to be dosed 6 hours after venetoclax administration, after completion of the 6- hour sample collection)
4, 6	1, 14 (± 3 days)	anytime during clinic visit	
Every 3 cycles thereafter	1, 14 (± 3 days)	anytime during clinic visit	

DDI Assessment: Venetoclax exposure (when co-administered with voruciclib) will be compared to historical single agent data to assess DDI and the effect of voruciclib on venetoclax pharmacokinetics. Venetoclax concentrations on Cycle 2 Day 1 and Cycle 1 Day 14 will also be compared assuming limited effect, if any, on voruciclib on Cycle 2 Day 1.

Voruciclib PK and other relevant data from all clinical trials (including late phase clinical trials) will be pooled and analyzed using population PK methods. Additionally, voruciclib exposure-response and exposure-safety assessments will be performed and the results will be presented in a separate report.

PK of voruciclib in subjects receiving co-administered azole antifungals versus those without azole antifungals will be compared.

Detailed instructions on collection of plasma for determination of voruciclib and venetoclax will be provided in the Site Laboratory Manual.

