APPENDIX 3. SCHEDULE OF ASSESSMENTS - AML SUBJECTS ONLY – COMBINATION THERAPY (CONTINUED)

Abbreviations: AML = acute myeloid leukemia; ALP = alkaline phosphatase; ALT = alanine aminotransferase; ANC = absolute neutrophil count; aPTT = activated partial thromboplastin time; AST = aspartate aminotransferase; BP = blood pressure; BUN = blood urea nitrogen; CBC = complete blood count; CR = complete response; CT = computed tomography; ECG = electrocardiogram; ECOG = Eastern Cooperative Oncology Group; EOS = End of Study; Hct = hematocrit; HCV Ab = hepatitis C virus antibody; Hgb = hemoglobin; HIV = human immunodeficiency virus; HR = heart rate; ICF = informed consent form; INR = international normalized ratio; LDH = lactate dehydrogenase; MCH = mean corpuscular hemoglobin; PCR = polymerase chain reaction; PD = pharmacodynamic; PK = pharmacokinetic; PT = prothrombin time; RBC = red blood cell; RU = ramp-up; TLS = tumor lysis syndrome; WBC = white blood cell.

- a. **Study Assessment Day(s)** – C1D1 and visits when blood for pharmacodynamic/biomarker studies are collected should be conducted Monday through Wednesday if possible so that specimens can be shipped for receipt no later than a Friday. There is \pm 3-day window allowable for each clinic visit during Cycle 1. Following Cycle 1, the allowable window is up to 7 days prior and 2 days after the scheduled clinic visit and its associated assessments.
- b. **Screening** – Screening assessments are to be performed within 28 days before the first dose of venetoclax. Laboratory assessments need not be repeated on Day 1 if performed within the prior 72 hours. Physical examination need not be repeated on Day 1 if performed within the prior 7 days. Some tests performed prior to obtaining ICF (e.g., CT scan, bone marrow biopsy) may not need to be repeated for the study as long as they were performed within the allowed screening window.
- c. **Venetoclax Ramp-up** – applies to **combination Cohorts 12–19 and 21–25**. Venetoclax ramp-up dosing begins on Cycle 1 Day 1 at 100 mg and 200 mg on Day 2. Dosing continues at 200 mg on Days 3–21, then 400 mg on Days 22–28. Increasing venetoclax dose from 200 mg to 400 mg on Day 22 is not considered dose ramp-up.
- d. **Cycle 3 and subsequent cycles** – all cycles after Cycle 3 should follow the same schedule of activities as Cycle 3.

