### **8.8 Analyses of Pharmacokinetics and Pharmacodynamics**

Analyses of pharmacokinetics and pharmacodynamics data will be conducted separately. The respective analysis plans will be specified in separate documents.

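### The venetoclax interaction check in Protocol 9.14.2 compares a day after 200 mg dosing with a day after 400 mg dosing, and states no correction for the prior dose

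*Protocol*

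**What the plan says.** Protocol 4.3.2.1 sets Cycle 1 venetoclax, after 100 mg on Day 1, at "200 mg on Days 2–21, then 400 mg administered as a single agent on Days 22–28". Cycle 2 restarts at 200 mg. Voruciclib ends on Day 14 in the IS2w,2w cohorts. In Cohorts 21–25 (IS3w,1w), "Voruciclib dosing will be administered on Days 3–21 at the appropriate Cohort Dose".

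Protocol 9.14.2 (Table 17) takes a venetoclax profile on C1D14 with voruciclib, and pre-dose, 2, 4 and 6 h samples on C2D1 before that day's voruciclib. In Cohort 12 (Table 16) the serial profile is on Day 13, and Day 14 has a pre-dose sample only. Two interaction comparisons are planned:

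- "Venetoclax exposure (when co-administered with voruciclib) will be compared to historical single agent data".
- "Venetoclax concentrations on Cycle 2 Day 1 and Cycle 1 Day 14 will also be compared assuming limited effect, if any". Only voruciclib washout is assumed. No ratio direction and no prior-dose adjustment is stated.

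Protocol 10.5 adds that "modeling will also be used if sufficient data are available", without naming carry-over. SAP 8.8 defers PK: "The respective analysis plans will be specified in separate documents". Appendix 3, footnote a, says that after Cycle 1 "the allowable window is up to 7 days prior and 2 days after the scheduled clinic visit".

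Protocol 4.3.2.2 reports, as preliminary, no voruciclib effect on venetoclax PK in Cohorts 12–15, without saying which comparison showed it. It justifies 400 mg on Days 22–28 in Cohorts 21–25 on two grounds: that lack of steady-state interaction, and very low voruciclib levels a week after the last dose.

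**The concern.** C2D1 serves as the off-voruciclib reference, but it differs from C1D14 in venetoclax history as well as in voruciclib. Its pre-dose sample is a 400 mg trough. Its 2, 4 and 6 h samples carry that residue on top of a new 200 mg dose. Normalising to the dose given on the day changes nothing, because both days are 200 mg.

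The protocol expects voruciclib, if anything, to raise venetoclax exposure through CYP3A4. The carry-over works against seeing that rise, and at trough it is about as large as the predicted effect. This is the only within-subject check the protocol specifies on whether voruciclib changes venetoclax exposure, and it serves a secondary PK objective.

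**Working it through.** **1. The plan's own figures.** Protocol 4.3.2.2 predicts a midazolam AUC ratio of 2.03 at voruciclib 50 mg. From its inputs:

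- Liver inhibitor level: 0.05 × (0.225 + 0.8 × 0.67 × 50/97) = 0.0251 mg/L. Gut level: 0.8 × 0.67 × 50/18 = 1.489 mg/L.
- Remaining enzyme fraction, kdeg/(kdeg + I × kinact/(I + KI)): liver 0.755, gut 0.091.
- Gut factor 1/(0.091 × 0.4 + 0.6) = 1.571. Liver factor 1/(0.755 × 0.93 + 0.07) = 1.295. Product 2.03, as stated.
- Voruciclib half-life, 24 × ln 2 / (−ln(1 − 1/R)): 25.0 h for R = 2.06 and 37.1 h for R = 2.77, close to the stated 24–36 h.

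**2. Ratio with no interaction.** The documents give no venetoclax kinetics. Assumed: one compartment, linear, first-order absorption. Concentration is the sum over doses D of D × ka/(ka − ke) × (exp(−ke·x) − exp(−ka·x)), where x is the time since that dose. Doses: 100 mg Day 1, 200 mg Days 2–21, 400 mg Days 22–28, 200 mg on C2D1. AUC0-6 is the trapezoid at 0, 2, 4 and 6 h.

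Example, half-life 19 h and ka 0.3/h (arbitrary units):

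| | 0 h | 2 h | 4 h | 6 h | AUC0-6 |
|---|---|---|---|---|---|
| C1D14 | 162 | 238 | 269 | 276 | 1451 |
| C2D1 | 325 | 389 | 409 | 406 | 2326 |
| Ratio | 0.50 | 0.61 | 0.66 | 0.68 | 0.62 |

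Over ka 0.1–1.0/h:

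| Half-life | Pre-dose ratio | AUC0-6 ratio |
|---|---|---|
| 14–26 h | 0.50 | 0.54–0.73 |
| 8–48 h | 0.50–0.52 | 0.54–0.86 |

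Using Day 13 for Cohort 12 gives the same results. The pre-dose figure hardly depends on the kinetics, because it is essentially 200/400.

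**3. What a 2.03-fold rise would read** (half-life 14–26 h, same ka range, if venetoclax behaved like midazolam):

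| Where the effect acts | Pre-dose C1D14/C2D1 |
|---|---|
| Bioavailability only | 1.02 |
| Gut/liver split 1.571 × 1.295 | 1.05–1.18 |
| Clearance only | 1.06–1.40 |

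On AUC0-6 the reading is about 1.1–1.5 across the three cases. Reduced clearance raises trough more than AUC, so the pre-dose reading of 1.40 stands for a true trough rise of about 1.40/0.50 = 2.8-fold.

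**4. When the shift changes.**

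- The inverse ratio, C2D1/C1D14, is biased upward by the same factor.
- A C2D1 visit seven days early falls on Day 22, before any 400 mg dose: ratio 1.00. At 14–26 h the pre-dose ratio is already 0.59–0.70 on Day 23 and 0.52–0.59 on Day 24.
- If venetoclax is held on Days 22–28, the AUC0-6 ratio rises to about 2.0–4.6 (half-life 12–36 h, ka 0.2/h).

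**5. Does the correction work?** At 14–26 h, pre-dose divided by prior daily dose gives 1.00–1.01. Subtracting half the C2D1 pre-dose value, decayed over the 6 h, removes the excess of 400 mg over 200 mg residue. AUC0-6 then gives 0.97–1.00 with the right half-life, and 0.94–1.04 with any half-life in that range.

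**6. Voruciclib washout (4.3.2.2).** Fraction left is 0.5^(t/half-life) at 24–36 h. At seven days, as measured on IS2w,2w (Day 14 to Day 21), it is 0.8–3.9%. At one day (Day 21 to Day 22 in Cohorts 21–25) it is 50–63%. At eight days (C2D1 in Cohorts 21–25) it is 0.4–2.5%, so the washout assumption for C2D1 itself is sound.

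**The case against.** **The PK plan may already handle this.** SAP 8.8 places the analysis in a separate document, where carry-over handling belongs, and 9.14.2 is mainly a sampling section. This stands as a limit. But 9.14.2 names the comparison and the one assumption it rests on, and that assumption leaves out the dose change.

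**The comparison is descriptive and secondary.** The historical comparison is listed first and does not share this bias, and modelling is foreseen. This stands, and it bounds the importance of the point.

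**The bias is not universal.** A reader might infer that carry-over always lowers the ratio. The documents do not support that. No ratio is defined, the visit window allows a Day 22 sample, and Table 11 requires venetoclax holds for severe cytopenias in subjects in remission at the end of Cycle 1. Venetoclax cuts with CYP3A inhibitors (Table 13) change it too.

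**The masking may be partial.** A 2.03-fold rise reads 1.02 pre-dose only if it scales every concentration equally. With part or all of it on clearance the reading is higher. Protocol 4.15 also says voruciclib did not inhibit midazolam hydroxylation in vitro and calls the enzyme parameters preliminary, so 2.03 is a benchmark for size, not a forecast for venetoclax.

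**The washout sentence is only one of two grounds.** If steady-state voruciclib does not alter venetoclax, residual voruciclib on Day 22 will not either. This stands within the doses studied.

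**Conclusion.** The mismatch is in the documents. Followed as written, with 400 mg taken on Days 22–28 up to the visit, a C1D14/C2D1 ratio is biased down to about 0.50 pre-dose and 0.54–0.86 on AUC0-6. The AUC range rests on assumed linear one-compartment kinetics (half-life 8–48 h, ka 0.1–1.0/h). An effect of the size the protocol predicts would be substantially understated, though not necessarily hidden.

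Two stronger readings are not supported. One is that the result reported for Cohorts 12–15 conceals a real rise: 4.3.2.2 does not say which comparison it used, and if it was the historical one this bias does not apply. The other is that 400 mg from Day 22 in Cohorts 21–25 is unsafe. There the point is wording only: 400 mg starts one day, not one week, after the last voruciclib dose, so the rationale rests on the lack of steady-state interaction. That is reported only up to 150 mg, and four of the five IS3w,1w levels (200–350 mg) exceed it.

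No DLT, MTD or mBED criterion is affected.

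**What to change.** **In 9.14.2 and the PK plan:**

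- Divide each pre-dose value by the preceding daily dose actually taken (400 vs 200 mg).
- Account for carry-over in the 2–6 h C2D1 samples, using actual dosing and sampling times.
- Flag or exclude subjects with holds or dose changes on Days 22–28.
- State which comparison supports the Cohorts 12–15 conclusion, and recheck it if it was the uncorrected one.

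**Where feasible, for remaining IS2w,2w subjects:** draw the existing, currently untimed C1D21 venetoclax sample pre-dose on Day 21, or on Day 22 before the first 400 mg dose. The prior dose is then 200 mg, voruciclib has been off for at least seven days, and the no-interaction ratio to C1D14 is 1.00. IS3w,1w has no such day, because Day 21 is still on voruciclib and 400 mg starts on Day 22. The correction or modelling is needed there.

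**In 4.3.2.2:** drop the one-week washout argument for Cohorts 21–25, and say that the reported interaction data stop at 150 mg.

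**Cost:** wording, plus a footnote to Table 17 and its Appendix 3 copy limited to IS2w,2w. No sample or visit is added. The re-timed draw means holding that morning's venetoclax and a tighter visit window. Day 21 is a Sunday if C1D1 is a Monday, which leaves Day 22 as the practical choice. Subjects past that visit can only be reanalysed.
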